7.2.2. Number of needle adjustments to reach the target and grading of adjustment

This secondary variable records the number and the grading of iterations required to finally reach the target. The number of needle placement adjustments to reach the target will be presented using frequency and percentage per trajectory or per needle, per lesion and per patient.

In addition, grading of adjustment will be presented using frequency and percentage per needle, per lesion and per patient.

7.2.3. Post-intervention ablation success using Minimal Ablative Margin (MAM) evaluation

For each lesion ablation, minimal distance between the lesion margin and the ablated area margin (mm) will be collected and summary statistics for quantitative parameters will be provided.

7.2.4. Long-term performance of the procedure using the local tumor progression (LTP) rate

Patients treated with tumor ablation are evaluated for Local tumor progression (LTP) on follow-up imaging by physician during the routine follow-up visits.

Frequency and percentage of patients with any visible local tumor progression on control imaging will be presented at approximately 2 months and 10 months. A 95% confidence interval will be provided for the percentage.

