| | 
notice and non-opposition forms discussed with the patient allowing them sufficient time to consider the study's implications before deciding whether to participate. Next visit planned (day of the CT-guided intervention).
 
• Visit 2: inclusion visit – procedure day D0
- Confirmation of the non-opposition by the investigator,- Collection of demographic data, tumor data, primary cancer data as well as other medical history. Collection of concomitants pathologies/treatments.- Patient placed under general anesthesia.- Acquisition of the pre-interventional CT-guided image for the planning phase.- Insertion of the needle(s) to the targeted area with the subject device.- Acquisition of the per-procedure image under CT guidance.- Validation of the correct positioning of the needle(s).- Acquisition of the post-interventional CT-guided image.• Visit 3: post-intervention follow-up visit at 2 months (D0+3 weeks≤D≤D0+3 months) Acquisition of an image (CT-guided or MRI) of the organ to evaluate ablation site recurrence (local tumor recurrence) and possible AEs.• Visit 4: post-intervention follow-up visit at 10 months (D0+6 months≤D≤D0+15 months) Acquisition of an image (CT-guided or MRI) of the organ to evaluate ablation site recurrence (local tumor recurrence) and possible AEs. |
| Study duration per patient | From patient's information and non-opposition form signature to visit 4. From 6 months to 16 months, depending on the day of patient's non-opposition confirmation and the day of the visit 4. |
| Study schedule | Planned start: Q1 2022 Planned recruitment time: 18 months Planned last patient out: Q1 2024 |
| Randomization/blinding | No randomization, open label |
| DSMB | Non |
| GCP statement | This study will be conducted in compliance with the protocol, the current version of the Declaration of Helsinki, the ICH-GCP and ISO EN 14155 as well as all national legal and regulatory requirements. |

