2.3.2. Secondary Performance Variables

- Needle placement accuracy per needle after adjustments:
 - Estimated distance from the needle tip to expected target point and
 - Estimated distance from the ablation center to targeted ablation center by operators.
- The number of needle adjustments to reach the target and the grading of adjustment
- Post-intervention ablation success using Minimal Ablative Margin (MAM) evaluation.
- Long-term performance of the procedure using the local tumor progression (LTP) rate at around 2 months and 10 months.
- User satisfaction (5-points Likert scale) via 4 questions.
- Device dysfunction (Yes/No)

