3.5.1. Summary statistics

Description of relevant study variables will be performed using n, number of missing data, mean, standard deviation, median, min and max for quantitative variables and using number of missing data, frequency and percentage of non-missing for qualitative variables.

Analyses will be presented by patient, by lesion (when relevant) and/or by needle (trajectory). The statistical analysis will take into account data clustering (e.g. several procedures for a given patient) in case of inferential statistics.

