5. DEMOGRAPHIC AND BASELINE CHARACTERISTICS

Demographic and tumor characteristics will be presented on ITT population using summary statistics for qualitative or quantitative parameters:

- Demographic data: age (years), gender, height (cm), weight (kg), Body Mass Index (kg/m²).
- Tumor characteristics: treated organ (liver, kidney or other), type of CT-Guided percutaneous treatment to be planned.
- Planning with the EPIONE device (number of needles trajectories, needle identification information).

Medical history, comorbidities, concomitant treatments and planning with the EPIONE device at inclusion will be described in patient data listings.

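### SAP 7.2.4 makes no use of further local treatment of the ablated site, so a site re-treated without a recorded LTP counts as LTP-free at 10 months

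*SAP*

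**What the plan says.** **The endpoint.** SAP 2.3.2 lists "Long-term performance of the procedure using the local tumor progression (LTP) rate at around 2 months and 10 months". SAP 7.2.4 states who is assessed and by what: "Patients treated with tumor ablation are evaluated for Local tumor progression (LTP) on follow-up imaging by physician during the routine follow-up visits". The summary is a crude percentage: "Frequency and percentage of patients with any visible local tumor progression on control imaging will be presented at approximately 2 months and 10 months". It is followed by "A 95% confidence interval will be provided for the percentage". Nothing in 7.2.4 says how a patient is counted when the ablated site received another local treatment before the image.

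**Treatment data.** The protocol synopsis has, under Visit 2 (procedure day), "Collection of concomitants pathologies/treatments". For Visits 3 and 4 it has "Acquisition of an image (CT-guided or MRI) of the organ to evaluate ablation site recurrence (local tumor recurrence) and possible AEs" and no treatment update. In the SAP, concomitant treatments appear in section 5: "Medical history, comorbidities, concomitant treatments and planning with the EPIONE device at inclusion will be described in patient data listings".

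**Visits.** SAP 2.2.1 sets Visit 3 at 3 weeks to 3 months and Visit 4 at 6 to 15 months after treatment. When several visits fall inside one window, the CRF takes only the last.

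**The concern.** The study is non-interventional and follows patients for up to 15 months after the procedure. No text restricts other treatment of the ablated site in that time. A site may be ablated again, resected or embolized because of residual tumor, a thin margin or a suspicious interim scan. If the next recorded image is clear, section 7.2.4 counts that patient as having no LTP. The table then cannot separate this patient from one whose ablation held unaided.

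This matters because LTP is the only performance variable that the SAP ties to the follow-up visits, and the SAP attributes it to the procedure. The error runs in the procedure's favour, and the planned confidence interval does not reflect it, since that interval describes sampling variation only.

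**Working it through.** **No figure to reproduce.** The documents give no expected LTP rate, no precision target and no number of ablation patients. The 55 patients include other procedures, such as biopsy. The check is therefore mainly a reading of the text, followed by an illustration.

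**Step 1: follow one patient through the stated rules.**
- D0: ablation. Treatments are collected (protocol, Visit 2).
- Visit 3 window: the recorded image shows no LTP. The patient counts as LTP-free at 2 months.
- Between recorded images: the site receives further local treatment. This can happen between 3 and 6 months, where no visit is recorded. It can also follow an earlier visit in a window, which SAP 2.2.1 leaves out of the CRF when a later one exists.
- Visit 4: the recorded image is clear. The patient stays in the denominator and adds nothing to the numerator.

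No supplied sentence changes that count.

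**Step 2: effect per patient.** With n ablation patients assessed at 10 months, each re-treated patient whose site would otherwise have shown LTP lowers the reported rate by 1/n.
- n = 30 (assumed): 1/30 = 3.3 points
- n = 40 (assumed): 1/40 = 2.5 points
- n = 55 (every patient an ablation, the upper limit): 1/55 = 1.8 points

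**Step 3: illustration of the bias.** Assume that 20% would show LTP without re-treatment, and that some of those sites are re-treated with no LTP recorded. The reported rate is (x − m)/n, where x is the number who would show LTP and m the number masked. Intervals are exact (Clopper-Pearson) 95%; the SAP names no method.

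| n | x | m | Reported rate | 95% CI |
|---|---|---|---|---|
| 40 | 8 | 0 | 8/40 = 20.0% | 9.1 to 35.6 |
| 40 | 8 | 2 | 6/40 = 15.0% | 5.7 to 29.8 |
| 40 | 8 | 4 | 4/40 = 10.0% | 2.8 to 23.7 |
| 30 | 6 | 3 | 3/30 = 10.0% | 2.1 to 26.5 |
| 55 | 11 | 6 | 5/55 = 9.1% | 3.0 to 20.0 |

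**Step 4: what a supportive row would show.** Assume 40 ablation patients, 8 with recorded LTP, and k others re-treated at the site without recorded LTP. The row reports (8 + k)/40.
- k = 0: 20.0% (9.1 to 35.6)
- k = 1: 9/40 = 22.5% (10.8 to 38.5)
- k = 4: 12/40 = 30.0% (16.6 to 46.5)

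Step 4 describes a different, composite endpoint. The gap between 20.0% and 30.0% is not an estimate of the error in the LTP rate, because some of the k patients may have been re-treated without progression.

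**The case against.** **Later treatment may be recorded already.** The protocol is a synopsis, the CRF is not supplied, the flow chart is not shown, and the SAP's section 13 listings are not in the text. Section 5 is a baseline section and would not describe follow-up data. This stands as far as it goes: one can say that no collection after Visit 2 is listed, not that none takes place. The analysis gap remains either way, because the SAP plans no use of such data.

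**Much re-treatment is already visible.** Section 7.2.3 summarises the ablative margin, so thin margins are shown, and LTP recorded at Visit 3 and then treated still appears in the 2-month figure. This narrows the point to sites re-treated with no LTP at any recorded visit. No text says how often that occurs.

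**Stronger readings that a reader might infer:**
- *Systemic therapy also spoils the rate, so LTP should be split by it.* In a single-arm, descriptive, non-interventional study, LTP under whatever systemic therapy follows is a legitimate treatment-policy summary. A split by therapy started after D0 conditions on something that progression itself may trigger, so it is confounded by indication, and the groups would be small.
- *A repeat procedure restarts D0 or inflates technical success.* SAP 3.5.1 says only "The statistical analysis will take into account data clustering (e.g. several procedures for a given patient) in case of inferential statistics". That is an example within a general statement on clustering and does not mention the same site. The protocol plans around 55 procedures in around 55 patients, and no text restarts D0.
- *The rate cannot be repaired after database lock.* Routine records at the one site could still be abstracted. Doing so once results are known is less satisfactory, but it is possible.
- *Every re-treated site is a failure, so the composite should lead.* Some re-treatment may be given without progression. A composite as main result would no longer measure LTP and could err upward.
- *The SAP calls a clear site a success.* It does not; section 7.2.4 defines no success category for LTP.

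**Conclusion.** The concern holds in a limited form. As written, section 7.2.4 counts a site re-treated between recorded images, with no LTP recorded, as LTP-free at 10 months, and so biases a rate labelled as long-term performance downward. The 2-month figure is less exposed.

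The size cannot be derived from the documents. It is 1/n for each affected patient whose site would otherwise have shown LTP. The values of n used here, the 20% rate and the numbers re-treated are all assumptions. The conclusion also rests on the supplied text being complete as to planned analyses. A CRF field for later treatment would reduce the data-collection part of the fix but not the analysis part. This is a worthwhile correction to a secondary endpoint and leaves the primary endpoint untouched.

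**What to change.** 1. If the CRF does not already do so, record at Visits 3 and 4, from the routine notes, any further local treatment of the ablated site since D0, with its date and reason.
2. In SAP 7.2.4, keep the imaging-only LTP rate with its 95% confidence interval as the main result.
3. Beside it, state how many ablation patients had the ablated site re-treated.
4. Add one supportive row, *LTP or further local treatment of the ablated site since D0*, with its 95% confidence interval.

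**Cost.** One abstracted item (occurrence, date and reason) per follow-up visit at one site, and one extra row. No visit, image or reader is added, and nothing is prescribed for patient care. The supportive rate can only equal or exceed the imaging-only rate, so it may look less favourable, and it may count some re-treatment given without progression. Recording the reason lets a reader judge how much.

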2. CLINICAL INVESTIGATION PLAN SUMMARY

2.1. Study objectives

Primary objective:

The primary objective of the study is to describe the performance related to the CT-guided procedure performed with the use of the Quantum Surgical EPIONE® device in the abdomen of the patient.

The primary endpoint is the technical success of each procedure. Technical success is defined in Section 9.1.1. The target is considered to have been reached when the needle(s) is(are) positioned accurately enough to allow the procedure to be carried out.

Secondary objectives:

The secondary performance objectives are as follows:

- Assessment of the needle placement accuracy through an estimation of the distance from the needle inserted and the predefined planning.
- Assessment of the number and the grading of needle readjustments to reach the target (minor, moderate, major).
- Assessment of post-intervention ablation success (ablation only).
- Assessment of the long-term performance of the procedure (local tumor progression rate).
- User satisfaction.
- Assessment of device's dysfunction.

The secondary safety objectives are as follows:

The safety objective is to assess the safety of the device, based on all adverse events (AEs) related to the device or the procedure, including Serious Adverse Events.

The investigator will describe the AE occurrence on a 2-point scale: "no major adverse event related to the CT-guided procedure" or "major adverse event related to the CT-guided procedure".

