2.2. Study design

2.2.1. Study design and device

This is a prospective, non-comparative, non-interventional Post Market Clinical Follow-up (PMCF) study.

A total of 55 patients with indication for percutaneous CT-guided procedure in the abdomen will be included at one site in France (Gustave Roussy Institute, Paris) where the EPIONE® device is used routinely.

The operating principle of the investigational device is as follows:

- Pre-interventional CT-scan image acquisition.
- Planning with the device's software (choice of needle(s)' trajectory(ies) to reach the targeted point).
- Needle(s) insertion according to the pre-defined planning.
- Acquisition of a per-procedure CT-scan image to evaluate the needle(s) placement.

Four visits will be recorded in the CRF.

In case of several follow-up visits with the timeslots of Visits 3 and 4, only the last one will be reported in the CRF:

- **Visit 1** (within one month before treatment): the first visit is planned to screen the patient, present the study, and deliver the information notice and informed consent form.
- **Visit 2** (treatment): the second visit consists of recovery of the signed informed consent form, and the realization of the prescribed CT-guided intervention by the radiologist.
- **Visit 3:** Follow-up at 2 months (between 3 weeks to 3 months after treatment).
- **Visit 4:** Follow-up at 10 months (between 6 months to 15 months after treatment), end of study.

Patients who are scheduled for an EPIONE® CT-guided procedure in the abdomen will be enrolled in the study. Eligible patient from the investigator's site will be proposed to participate.

The inclusion period is estimated as 18 months for 55 patients. The study was initiated with the only one site for which the EPIONE® device is routinely used.

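### The 10-month LTP percentage is not read against the Visit 3 result, so it cannot separate disease already present at Visit 3 from new progression

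*SAP*

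**What the plan says.** SAP 2.1 lists two separate secondary objectives for ablation: "Assessment of post-intervention ablation success (ablation only") and "Assessment of the long-term performance of the procedure (local tumor progression rate"). SAP 2.3.2 places both follow-up times under the second: "Long-term performance of the procedure using the local tumor progression (LTP) rate at around 2 months and 10 months".

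SAP 7.2.4 names the population and the assessor: "Patients treated with tumor ablation are evaluated for Local tumor progression (LTP) on follow-up imaging by physician during the routine follow-up visits". The analysis is: "Frequency and percentage of patients with any visible local tumor progression on control imaging will be presented at approximately 2 months and 10 months". The section also plans an interval at the 95% level, without naming its method.

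The visit windows are in SAP 2.2.1: "Follow-up at 2 months (between 3 weeks to 3 months after treatment") and "Follow-up at 10 months (between 6 months to 15 months after treatment), end of study". If a patient has several visits in a window, only the last is entered in the CRF.

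The protocol synopsis describes the imaging at Visits 3 and 4 in identical terms: "to evaluate ablation site recurrence (local tumor recurrence) and possible AEs".

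Completeness of ablation is addressed in SAP 7.2.3 through the minimal ablative margin (MAM). It is summarized in mm, with no success threshold and no link to LTP.

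**The concern.** Recurrence or progression at an ablated site is normally understood relative to a site that was clear. The SAP text does not require a clear scan before a finding counts as LTP, has no category for residual tumor, and does not say how a patient positive at Visit 3 counts at Visit 4. The Visit 3 window opens three weeks after treatment, so a positive scan there may be residual tumor or early recurrence.

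For a needle-guidance device the two findings point to different things. Tumor already visible at Visit 3 bears mainly on placement or coverage on the day. Tumor newly visible at Visit 4 after a clear Visit 3 scan is the long-term outcome. Two unlinked percentages do not show how many Visit 4 positives are new. The long-term objective could be answered with a figure that partly repeats the 2-month result, or one from which early failures have dropped out.

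**Working it through.** **Inputs from the documents.** The measure is a patient-level percentage at each of two times (SAP 7.2.4). Percentages are of non-missing values (SAP 3.5.1) and LTP status is not imputed (SAP 3.5.4). The sample is 55 patients (SAP 2.2.1) across procedure types that include biopsy (protocol synopsis, Indication), so the LTP denominator is at most 55. No LTP rate is stated, so there is no plan figure to reproduce.

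**Assumptions, not in the documents.** 30, 45 or 55 ablation patients; about 0%, 5% or 10% positive at Visit 3; about 10% of the rest newly positive at Visit 4. Everyone is scanned at both visits unless stated. Intervals are exact (Clopper-Pearson) 95%.

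**Step 1: what the two planned percentages determine.** Let *a* be the number positive at Visit 3, *b* at Visit 4, and *k* at both, with *n* patients. New cases at Visit 4 are *b − k*, and *k* can be anything from max(0, *a + b − n*) to min(*a*, *b*). Take *n* = 45, *a* = 3, *b* = 6. The SAP reports 3/45 = 6.7% (1.4 to 18.3%) and 6/45 = 13.3% (5.1 to 26.8%). Since *k* may be 0 to 3, new cases are 3 to 6. The rate among those clear at Visit 3, (*b − k*)/(*n − a*), is anywhere from 3/42 = 7.1% (1.5 to 19.5%) to 6/42 = 14.3% (5.4 to 28.5%). The same pair of published percentages fits either.

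**Step 2: how Visit 3 positives move the 10-month figure.** Let *r* be positive at Visit 3 and *m* newly positive at Visit 4. Take *n* = 55, *r* = 6, *m* = 5. Visit 3 is 6/55 = 10.9% (4.1 to 22.2%) throughout.

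- All *r* persist and are counted: (*r + m*)/*n* = 11/55 = 20.0% (10.4 to 33.0%).
- All *r* are cleared before Visit 4 and counted negative: *m*/*n* = 5/55 = 9.1% (3.0 to 20.0%).
- All *r* have no Visit 4 scan and leave the non-missing denominator: *m*/(*n − r*) = 5/49 = 10.2% (3.4 to 22.2%).
- New progression among those clear at Visit 3: *m*/(*n − r*) = 5/49 = 10.2%.

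The third case matches the fourth only because every Visit 3 positive happens to be missing. The planned output would not show this, nor that 11 of 55 had been positive at some visit.

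**Step 3: range over the assumptions.**

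| n | r | m | Visit 4, r persist | Visit 4, r cleared | New among clear at Visit 3 |
|---|---|---|---|---|---|
| 30 | 2 | 3 | 5/30 = 16.7% | 3/30 = 10.0% | 3/28 = 10.7% |
| 30 | 3 | 3 | 6/30 = 20.0% | 3/30 = 10.0% | 3/27 = 11.1% |
| 45 | 2 | 4 | 6/45 = 13.3% | 4/45 = 8.9% | 4/43 = 9.3% |
| 45 | 4 | 4 | 8/45 = 17.8% | 4/45 = 8.9% | 4/41 = 9.8% |
| 55 | 3 | 5 | 8/55 = 14.5% | 5/55 = 9.1% | 5/52 = 9.6% |
| 55 | 6 | 5 | 11/55 = 20.0% | 5/55 = 9.1% | 5/49 = 10.2% |

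Against the last column, the 10-month figure is 4.0 (13.3 − 9.3) to 9.8 (20.0 − 10.2) points higher if Visit 3 positives persist. It is 0.4 (8.9 − 9.3) to 1.1 (9.1 − 10.2) points lower if they are cleared. With no Visit 3 positives all three columns agree, for example 6/55 = 10.9% at *n* = 55.

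**The case against.** A reader might infer that the SAP counts every visible tumor as LTP, so that residual tumor is wrongly classified by design. The text does not say that. It counts visible local tumor progression as judged by the physician, and the protocol speaks of recurrence. A physician could leave residual tumor out. This part of the objection stands: misclassification is possible because the supplied text gives no rule, but it is not planned.

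A reader might also infer that early and late findings are pooled. They are not. The 2-month percentage is presented on its own, so the difficulty lies with the 10-month figure.

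Nor is it right that the plan has no information on same-day failure. A post-interventional CT is taken on the procedure day and MAM is a separate endpoint. What remains is that MAM is summarized only as a distance and is not set against later imaging.

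It would be equally wrong to call every Visit 3 positive residual tumor. The window runs to three months and only its last visit is recorded, so some positives may be early recurrence.

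The CRF and the content of the patient listings are not in the supplied text, and either might record a residual-tumor item. Patient listings could let a reader trace individual cases, but they are not a planned rate with an interval. Finally, this is a descriptive secondary endpoint in a single-arm study with no threshold attached, and the intervals above overlap widely. That limits the consequence but does not make the 10-month percentage interpretable as a long-term rate.

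**Conclusion.** The concern holds in a limited form. SAP 7.2.4 presents LTP at two times without requiring an earlier clear scan and without using Visit 3 status at Visit 4. The 10-month percentage can therefore carry forward disease already present at Visit 3, or lose Visit 3 positives who were cleared or not scanned again. The output will not show which occurred.

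Its size and direction cannot be derived from the documents. In the illustrations the 10-month figure lies between 1.1 points below and 9.8 points above the rate of new progression. That range rests wholly on the assumed ablation numbers, Visit 3 positivity and new-progression rate, and on all Visit 3 positives behaving alike. If no patient is positive at Visit 3, and all are scanned at both visits, the issue disappears. This is an inexpensive improvement to a secondary analysis, not a flaw in the primary endpoint.

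**What to change.** Keep both planned percentages. Add to SAP 7.2.4 a Visit 3 by Visit 4 cross-tabulation in ablated patients, and by lesion where lesion-level results are recorded. Report two rates with 95% confidence intervals:

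- **(a)** Local tumor visible at the recorded Visit 3 scan, labelled early local failure (residual tumor or early recurrence) and shown beside the MAM result.
- **(b)** Local tumor newly visible at Visit 4 among those clear at Visit 3, reported as the long-term LTP rate.

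Show missing Visit 3 and missing Visit 4 scans as separate categories. Flag Visit 3 positives who were re-treated before Visit 4, where this is recorded. Any lesion-level interval should allow for several lesions in one patient, as SAP 3.5.1 already foresees for clustered data.

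The cost is one more table and a few lines of SAP text, using visit results already planned, with no extra scans or patients. The downside is a slightly smaller denominator for (b), for example 49 instead of 55 in the illustration.
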